8.1 BEST OVERALL RESPONSE (BOR) AND OBJECTIVE RESPONSE RATE (ORR) PER RECIST v1.1

Responses to the study treatment are categorized per RECIST 1.1 as the following (from the best to the worst): complete response (CR), partial response (PR), stable disease (SD), progressive disease (PD) and not evaluable (NE).

Per RECIST 1.1, the best overall response (BOR) for a subject is the best response of CR, PR, SD, PD and NE observed from the first dose of study drug until PD or the end of

treatment, whichever occurs earlier. The objective response rate (ORR) is the proportion of subjects whose BOR is either CR or PR.

8.2 iBOR AND iORR PER iRECIST

iRECIST is based on RECIST 1.1 but adapted to account for the unique tumor response seen with immunotherapeutic drugs. iRECIST introduces new criteria of unconfirmed progressive disease (iUPD) and confirmed progressive disease (iCPD) to prevent the discontinuation of study treatment in cases of pseudoprogression. Immune responses assigned by the iRECIST criteria are (from the best to the worst): complete response (iCR), partial response (iPR), stable disease (iSD), unconfirmed progressive disease (iUPD), confirmed progressive disease (iCPD) and not evaluable (NE).

There is no distinct iRECIST assessment until radiographic disease progression based on RECIST 1.1. For participants who show evidence of radiological PD by RECIST 1.1 as determined by the Investigator, the Investigator will decide whether to continue a participant on study treatment until repeat tumor imaging is obtained for confirmation of PD by iRECIST.

Per iRECIST, the best overall response (iBOR) for a subject is the best response of iCR, iPR, iSD, iUPD, iCPD and NE observed from the first dose of study drug until iCPD or the end of treatment, whichever occurs earlier. The objective response rate (iORR) is the proportion of subjects whose iBOR is either iCR or iPR.

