- t) Dipstick is acceptable. Microscopic analyses if dipstick is abnormal. No need to repeat on Cycle 1 Day 1 if screening assessment performed within 72 hours prior to that date. If  $\geq 2+$  protein on urine dipstick, then collect spot urine sample to calculate urine protein to creatinine ratio.
- u) Tumor assessments will be performed at Screening, Cycle 4 Day 1, then every 9 weeks for 1 year following the first dose of study drug, and every 12 weeks for the second year. Scans within 28 days of Cycle 1 Day 1, prior to signing the ICF, can be used as the screening scan. On-treatment scans can be obtained  $\pm 7$  days. The same modality (CT, PET/CT or MRI) should be used throughout the study for a given patient. Collection of images will be obtained for retrospective analysis. Central review of scans may be performed during the study.

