## 6.6 Measures to Minimize Bias: Randomization and Blinding

Part 1 of this study is a single arm non-randomized study.

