**Non-target lesions**

All other lesions (or sites of disease) including pathological lymph nodes (with short axis  $\geq 10$  mm and  $< 15$  mm) should be identified as non-target lesions and should also be recorded at baseline. Measurements are not required and these lesions should be followed as ‘present,’ ‘absent,’ or in rare cases ‘unequivocal progression’ (more details to follow). In addition, it is possible to record multiple non-target lesions involving the same organ as a single item on the Case Report Form (e.g., ‘multiple enlarged pelvic lymph nodes’ or ‘multiple liver metastases’).

**Response Criteria:** The BOR is the best response recorded from the start of the study treatment until the end of treatment. The subject’s BOR assignment will depend on the findings of both target and non-target disease and will also take into consideration the appearance of new lesions.

**Complete Response (CR):** Disappearance of all target lesions. Any pathological lymph nodes (whether target or non-target) must have decreased in size to have a short axis of  $< 10$  mm.

**Partial Response (PR):** At least a 30% decrease in the sum of diameters of target lesions taking as reference the baseline sum diameters.

**Stable Disease (SD):** Neither sufficient shrinkage to qualify for PR nor sufficient increase to qualify for progressive disease (PD), taking as reference the smallest sum diameters while on study.

**Non-CR/Non-PD:** Persistence of one or more non-target lesion(s) and/or maintenance of tumor marker level above the normal limits.

**Progressive Disease (PD):** At least a 20% increase in the sum of diameters of target lesions, taking as reference the smallest sum on study (this includes the baseline sum if that is the smallest on study). In addition to the relative increase of 20%, the sum must also demonstrate an absolute increase of at least 5 mm. For non-target lesions, unequivocal progression (see comments below) of existing lesions represents PD. Note: the appearance of one or more new lesions is also considered progression.

Lymph nodes identified as target lesions should always have the actual short axis measurement recorded (measured in the same anatomical plane as the baseline examination), even if the nodes regress to below 10 mm on study. This means that when lymph nodes are included as target lesions, the 'sum' of lesions may not be zero even if CR criteria are met, since a normal lymph node is defined as having a short axis of <10 mm.

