## Comparison of RECIST 1.1 and iRECIST Criteria

	RECIST 1.1	iRECIST
Definitions of measurable and non-measurable disease; numbers and site of target disease	Measurable lesions are $\geq 10$ mm in diameter ( $\geq 15$ mm for nodal lesions); maximum of five lesions (two per organ); all other disease is considered non-target (must be $\geq 10$ mm in short axis for nodal disease)	No change from RECIST 1.1; however, new lesions are assessed as per RECIST 1.1 but are recorded separately on the case report form (but not included in the sum of lesions for target lesions identified at baseline)
Complete response, partial response, or stable disease	Cannot have met criteria for progression before complete response, partial response, or stable disease	Can have had iUPD (one or more instances), but not iCPD, before iCR, iPR, or iSD
Confirmation of complete response or partial response	Only required for non-randomised trials	As per RECIST 1.1
Confirmation of stable disease	Not required	As per RECIST 1.1
New lesions	Result in progression; recorded but not measured	Results in iUPD but iCPD is only assigned on the basis of this category if at next assessment additional new lesions appear or an increase in size of new lesions is seen ( $\geq 5$ mm for sum of new lesion target or any increase in new lesion non-target); the appearance of new lesions when none have previously been recorded, can also confirm iCPD
Independent blinded review and central collection of scans	Recommended in some circumstances —eg, in some trials with progression-based endpoints planned for marketing approval	Collection of scans (but not independent review) recommended for all trials
Confirmation of progression	Not required (unless equivocal)	Required
Consideration of clinical status	Not included in assessment	Clinical stability is considered when deciding whether treatment is continued after iUPD

"i" indicates immune responses assigned using iRECIST. RECIST=Response Evaluation Criteria in Solid Tumours. iUPD=unconfirmed progression. iCPD=confirmed progression. iCR=complete response. iPR=partial response. iSD=stable disease.

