3.4 RESPONSE/SURVIVAL FOLLOW-UP PERIOD

Subjects who do not experience progressive disease prior to treatment discontinuation will continue to have radiologic and clinical tumor assessments every 9 weeks for the first year and every 12 weeks during the second year until progression is confirmed, consent withdrawal, start of a new anti-cancer treatment, loss to follow-up, or death, whichever comes first. These subjects will also be followed by telephone every 12 weeks during the second year. The duration for response/survival follow-up is approximately 2 years from the first dose of study drug.

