8 EFFICACY ANALYSIS

The efficacy evaluable analysis set will be used for the efficacy summary.

The anti-tumor efficacy of the combination of TJ004309 and atezolizumab will be summarized by best of response (BOR) and objective response rate (ORR) assessed by the Response Evaluation Criteria in Solid Tumors (RECIST 1.1) and immune RECIST (iRECIST) guidelines. All tumor response data (including unscheduled tumor assessments) will be used in the efficacy analysis.

Efficacy endpoints such as duration of response (DOR), progression-free survival (PFS) and overall survival (OS) will not be reported due to the abbreviated nature of the CSR to be produced.

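### The SAP counts a single unconfirmed CR or PR as a response in ORR and iORR, although the protocol's Appendix 1 requires confirmation in a non-randomised trial

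*SAP*

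**What the plan says.** **SAP 8.1 (RECIST 1.1).** A subject's BOR "is the best response of CR, PR, SD, PD and NE observed from the first dose of study drug until PD"; the window closes sooner if treatment stops first. ORR is the proportion with a BOR of CR or PR.

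**SAP 8.2 (iRECIST).** iBOR is built in the same way, with iCPD in place of PD. "The objective response rate (iORR) is the proportion of subjects whose iBOR is either iCR or iPR". The section describes confirmation of progression (iUPD and iCPD) but not confirmation of response.

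**SAP 8.3.** The efficacy summary gives the observed ORR and iORR with Clopper-Pearson intervals, and does not separate confirmed from unconfirmed responses.

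**Protocol Appendix 1, comparison of RECIST 1.1 and iRECIST.** The row on confirming a complete or partial response reads "Only required for non-randomised trials" for RECIST 1.1. The iRECIST column refers back to the RECIST 1.1 rule.

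**Protocol 6.6.** "Part 1 of this study is a single arm non-randomized study".

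**Protocol Appendix 1, Response Criteria.** "The BOR is the best response recorded from the start of the study treatment until the end of treatment". Neither this text nor the CR and PR definitions beside it mention confirmation.

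**The concern.** ORR by RECIST 1.1 is the primary endpoint and ORR by iRECIST is a secondary one. As the SAP is written, a subject whose tumour shrinks past the PR threshold on one scan and not on the next is a responder for good. The protocol's own criteria table says that a trial of this kind should require a second assessment.

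There is no control arm in which the same leniency would operate, so any excess goes straight into the reported rate. The usual safeguard is also missing. SAP 8 states: "Efficacy endpoints such as duration of response (DOR), progression-free survival (PFS) and overall survival (OS) will not be reported". No item in the SAP 8.3 summary would therefore show whether a counted response outlasted one scan.

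Nothing is claimed here about the decision on Part 2. SAP 4.1 records that Part 2 was not initiated. What is at stake is the ORR, the iORR and their intervals in the clinical study report.

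**Working it through.** The plan states no figure that depends on this point, so there is none to reproduce. The check is a comparison of the texts, followed by illustrations of size.

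**1. Does the confirmation rule apply?** The opening of Appendix 1 adopts RECIST 1.1 and iRECIST for this study. Its table requires confirmation of CR and PR when a trial is not randomised, under both criteria. Protocol 6.6 says Part 1 is not randomised. The condition is met for ORR and for iORR.

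**2. Does the SAP apply it?** A confirmed-response rule needs a second assessment, a minimum interval, and a category for a CR or PR that is not confirmed. SAP 8.1 and 8.2 give none of the three. The operative word is observed, and SAP 8.3 uses it again for the rates.

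**3. Direction.** Let x be the subjects with any observed CR or PR, u those among them never confirmed, and n the evaluable subjects. Then

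- ORR as the SAP defines it = x/n
- confirmed ORR = (x − u)/n
- difference = u/n, which is never negative

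**4. Size.** Each unconfirmed response is worth 100/n points: 100/15 = 6.7 and 100/30 = 3.3. The value 15 is the Cohort 1 futility look and 30 is the maximum cohort size (SAP 3.1). The exact 95% limits, by the method in SAP 8.3, are the 0.025 quantile of Beta(x, n−x+1) and the 0.975 quantile of Beta(x+1, n−x), with a lower limit of 0 when x = 0. With u = 1:

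| Any response counted | One response not confirmed |
|---|---|
| 3/15 = 20.0% (4.3 to 48.1) | 2/15 = 13.3% (1.7 to 40.5) |
| 2/15 = 13.3% (1.7 to 40.5) | 1/15 = 6.7% (0.2 to 31.9) |
| 4/30 = 13.3% (3.8 to 30.7) | 3/30 = 10.0% (2.1 to 26.5) |
| 1/30 = 3.3% (0.1 to 17.2) | 0/30 = 0% (0 to 11.6) |

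The documents give neither the number of responders nor the share unconfirmed, so u = 1 and these counts are assumptions. SAP 4.1 says responses were too few to start Part 2, which makes the low-count rows the more relevant ones.

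**5. Can the existing scans confirm a response?** Protocol Table 2, footnote u: "Tumor assessments will be performed at Screening, Cycle 4 Day 1, then every 9 weeks for 1 year", with on-treatment scans allowed 7 days either side. Nine weeks is 63 days, so consecutive first-year scans are between 63 − 14 = 49 and 63 + 14 = 77 days apart. Any such pair exceeds a 4-week (28-day) minimum. Imaging also goes on after treatment stops without progression (SAP 3.4): "Subjects who do not experience progressive disease prior to treatment discontinuation will continue to have radiologic and clinical tumor assessments every 9 weeks".

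**The case against.** **Confirmation may be incorporated by reference.** SAP 8 says response is assessed by the RECIST 1.1 and iRECIST guidelines, and both definitions open by invoking the criteria. A sponsor could say that confirmation comes with them. But an explicit definition follows, and that is what a programmer will code. Even if confirmation is implied, two analysts could reach different rates, because the interval and the fallback category are not stated.

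**The requirement is one row of a generic table.** This is partly right. Other rows of that table are general guidance, and the study-specific BOR text in the same appendix has no confirmation condition, so SAP 8.1 is consistent with that text. The protocol therefore has a gap of its own. Still, the table row is the only protocol text on confirming a response, and for this design it says yes.

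**A listing would show durability.** Protocol 9.2.4 promises tumour measurements by subject and time, and SAP 4.1 provides for listings. With few responders, a reader could work out confirmation from them. That softens the point, but the headline rate stays as it is, and SAP 8 does not name the listing.

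**The stakes are modest and the change comes late.** There is no formal sample-size basis and no test of ORR, and the report is an abbreviated one. The SAP was written after the Part 1 responses were broadly known. This is fair, and it argues for showing both counts. The rule itself comes from the protocol's own appendix and can only lower the rate, so adopting it does not favour the treatment.

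**Missing scans become non-response.** With 9-weekly imaging, a responder who dies, withdraws or starts new therapy before the next scan cannot be confirmed. This stands as a real cost, and it is why unconfirmed responses need a row of their own.

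**Conclusion.** The concern holds. SAP 8.1 and 8.2 count an unconfirmed CR or PR, and the protocol's Appendix 1 table requires confirmation for a non-randomised trial under both sets of criteria. The fault is shared: the Appendix 1 text on best response is also silent, so it must be reconciled with the table as well as with the SAP.

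The bias runs one way and equals 100/n points per unconfirmed responder. The textual gap is certain. The size is not, because it depends on how many responses were unconfirmed. If every response was confirmed, or there were none, no number changes; but the SAP 8.3 summary would not let a reader know that. This should be fixed before the report is written. The end-of-treatment window in SAP 8.1 agrees with the protocol text and is not in question.

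**What to change.** - **SAP 8.1 and 8.2:** count CR or PR (iCR or iPR) as best response only if a later assessment confirms it, before PD in 8.1 and before iCPD in 8.2. State a minimum interval; 4 weeks is a proposal, since the documents give none. State which category an unconfirmed CR or PR then takes.
- **Window:** keep the end-of-treatment limit for the first response. Say that a scan after treatment stops, but before any new anti-cancer therapy, may confirm an on-treatment response. Scheduled and unscheduled scans may both serve.
- **SAP 8.3:** add one row for unconfirmed CR/PR and one for unconfirmed iCR/iPR, so that both counts are visible.
- **Protocol Appendix 1:** align the BOR, CR and PR text with the comparison table.

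Merely labelling the current rates as unconfirmed and showing both counts would remove the ambiguity, but the primary rate would still depart from the Appendix 1 table.

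The cost is SAP wording, one protocol clarification and a re-derivation from scans already collected. The reported ORR may fall by 6.7 points per unconfirmed responder at n=15, or 3.3 at n=30. Because scheduled scans are 49 to 77 days apart, confirmation will in practice usually take 7 to 11 weeks unless an unscheduled scan exists.

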### *Assessment and Decision at RECIST 1.1 Progression*

For participants who show evidence of radiological PD by RECIST 1.1 as determined by the Investigator, the Investigator will decide whether to continue a participant on study treatment until repeat imaging is obtained using iRECIST for participant management. This decision by the Investigator should be based on the participant's overall clinical condition.

Clinical stability is defined as the following:

- Absence of symptoms and signs indicating clinically significant progression of disease
- No decline in ECOG performance status
- No requirements for intensified management, including increased analgesia, radiation, or other palliative care

Any participant deemed **clinically unstable** should be discontinued from study treatment at site-assessed first radiologic evidence of PD and is not required to have repeat tumor imaging for confirmation of PD by iRECIST.

If the Investigator decides to continue treatment, the participant may continue to receive study treatment and the tumor assessment should be repeated 4 to 8 weeks later to confirm PD by iRECIST, per Investigator assessment.

Tumor flare may manifest as any factor causing radiographic progression per RECIST 1.1, including:

- Increase in the sum of diameters of target lesion(s) identified at baseline to  $\geq 20\%$  and  $\geq 5$  mm from nadir
  - Note: the iRECIST publication uses the terminology "sum of measurements", but "sum of diameters" will be used in this protocol, consistent with the original RECIST 1.1 terminology.

- Unequivocal progression of non-target lesion(s) identified at baseline
- Development of new lesion(s)

iRECIST defines new response categories, including iUPD (unconfirmed progressive disease) and iCPD (confirmed progressive disease). For purposes of iRECIST assessment, the first visit showing progression according to RECIST 1.1 will be assigned a visit (overall) response of iUPD, regardless of which factors caused the progression.

At this visit, target and non-target lesions identified at baseline by RECIST 1.1 will be assessed as usual.

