#### *Confirmation of Progression*

Progression is considered confirmed, and the overall response will be iCPD, if ANY of the following occurs:

- Any of the factors that were the basis for the initial iUPD show worsening
  - For target lesions, worsening is a further increase in the sum of diameters of  $\geq 5$  mm, compared to any prior iUPD time point
  - For non-target lesions, worsening is any significant growth in lesions overall, compared to a prior iUPD time point; this does not have to meet the “unequivocal” standard of RECIST 1.1
  - For new lesions, worsening is any of these:
    - An increase in the new lesion sum of diameters by  $\geq 5$  mm from a prior iUPD time point
    - Visible growth of new non-target lesions
    - The appearance of additional new lesions
- Any new factor appears that would have triggered PD by RECIST 1.1

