#### *Resolution of iUPD*

Progression is considered not confirmed, and the overall response becomes iSD/iPR/iCR, if:

- None of the progression-confirming factors identified above occurs, AND
- The target lesion sum of diameters (initial target lesions) is not above the initial PD threshold.

The response is classified as iSD or iPR (depending on the sum of diameters of the target lesions), or iCR if all lesions resolve.

In this case, the initial iUPD is considered to be pseudo-progression, and the level of suspicion for progression is “reset”. This means that the next visit that shows radiographic progression, whenever it occurs, is again classified as iUPD by iRECIST, and the confirmation process is repeated before a response of iCPD can be assigned.

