8.3 PRESENTATION

The efficacy summary will include the following:

- Number and percentage of subjects who died before the first response assessment
- Number and percentage of subjects who had at least one response assessment per RECIST 1.1
- Number and percentage of each response (i.e. CR, PR, SD, PD, NE) as the best overall response per RECIST 1.1
- Observed objective response rate (per RECIST 1.1) and the 95% Clopper-Pearson confidence interval
- Number and percentage of subjects who had at least one response assessment per iRECIST
- Number and percentage of each response (i.e. iCR, iPR, iSD, iUPD, iCPD, NE) as the best overall response per iRECIST
- Observed objective response rate (per iRECIST) and the 95% Clopper-Pearson confidence interval

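### SAP 8.2 ranks iUPD above iCPD and takes the best response, so confirmed progression can never be a subject's iBOR and is reported as unconfirmed

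*SAP*

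**What the plan says.** SAP 8.2 lists the iRECIST categories in order from best to worst. The lower end of the list reads "stable disease (iSD), unconfirmed progressive disease (iUPD), confirmed progressive disease (iCPD) and not evaluable (NE"), so iUPD outranks iCPD. The selection rule follows: "the best overall response (iBOR) for a subject is the best response of iCR, iPR, iSD, iUPD, iCPD and NE observed". The window is "observed from the first dose of study drug until iCPD or the end of treatment, whichever occurs earlier". iORR counts only subjects whose iBOR is iCR or iPR.

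SAP 8.3 requires all six categories in the efficacy table: "Number and percentage of each response (i.e. iCR, iPR, iSD, iUPD, iCPD, NE) as the best overall response per iRECIST".

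The order in which the categories can occur is set in Protocol Appendix 1:

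- At first progression, "the first visit showing progression according to RECIST 1.1 will be assigned a visit (overall) response of iUPD", whatever caused it.
- Confirmation is judged at a later scan. It requires either that "Any of the factors that were the basis for the initial iUPD show worsening" or that a new factor appears which would itself be progression under RECIST 1.1.
- If the iUPD resolves as pseudo-progression, the next progression is again iUPD, and "the confirmation process is repeated before a response of iCPD can be assigned".

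**The concern.** A best-of rule works when the categories are alternative outcomes. iUPD and iCPD are successive stages of one outcome: a subject must pass through the first to reach the second. If the earlier stage is ranked as better, the later stage can never be selected.

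At stake is what two rows of the table mean. SAP section 8 drops DOR, PFS and OS from the abbreviated report, so the iBOR distribution and iORR are the iRECIST results that remain. SAP 4.1 says Part 2 was not started because there were too few responses, so the non-response rows may hold a good part of the table. A zero for iCPD would look like an observation when it is a product of the rule, and the row labelled unconfirmed would contain confirmed cases.

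**Working it through.** The plan gives no figure on this point, so there is nothing to reproduce. The check is logical, supported by an enumeration.

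**Inputs**

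- Rank (SAP 8.2): iCR 1, iPR 2, iSD 3, iUPD 4, iCPD 5, NE 6.
- Selection (SAP 8.2): iBOR is the smallest rank observed in the window.
- Window (SAP 8.2): first dose to the earlier of iCPD and end of treatment.
- Order (Protocol Appendix 1): iUPD comes before any iCPD, and this starts afresh after a reset.

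**Reasoning**

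1. Suppose a subject has iCPD in the window. By Appendix 1 an earlier visit was iUPD, and being earlier it also lies in the window.
2. The smallest rank is then at most 4. iCPD has rank 5, so it is never selected.
3. It makes no difference whether the iCPD visit itself counts as inside the window, because the iUPD is inside either way.
4. A pseudo-progression reset does not rescue the rule. The reset requires an iSD, iPR or iCR, each of which outranks both progression categories, and a new iUPD must still come before any iCPD.
5. If the first iUPD falls after end of treatment, a later iCPD is outside the window too.

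**Enumeration**

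All visit sequences of 1 to 6 assessments were generated. iCPD was allowed only while an iUPD was unresolved; iSD, iPR and iCR cleared a pending iUPD and NE did not; each sequence stopped at iCPD. These are counts of possible sequences, not expected patients.

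| | Sequences |
|---|---|
| Admissible | 20,505 |
| Ending in iCPD | 975 |
| of which iBOR = iCR | 522 |
| iBOR = iPR | 274 |
| iBOR = iSD | 122 |
| iBOR = iUPD | 57 |
| iBOR = iCPD | 0 |

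Check on the 57: for a sequence of length L ending in iCPD with nothing better than iUPD, the first L − 1 visits are each iUPD or NE, with at least one iUPD. That gives 2^(L−1) − 1 sequences. Summing over L = 1 to 6: 0 + 1 + 3 + 7 + 15 + 31 = 57.

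If confirmed progression is allowed to override iUPD when nothing better was seen, all 57 move to iCPD. The sequences with iCR or iPR as iBOR stay at 522 + 274 = 796, so iORR and its Clopper-Pearson interval are untouched.

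**Effect on the table**

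Let c be the confirmed progressors with no iCR, iPR or iSD, and u the other subjects with iUPD and nothing better.

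- As written: iUPD = c + u, iCPD = 0.
- With the override: iUPD = u, iCPD = c.

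The documents do not give c. It can lie anywhere from 0 to the number evaluable in a cohort, planned at up to 30. As an assumed illustration only: of 30 subjects, 18 progress at the first scan, 10 of them are re-imaged on treatment, 8 are confirmed, and the other 2 remain iUPD. Then c = 8 and u = 10. The rule reports iUPD 18/30 (60.0%) and iCPD 0; the override gives iUPD 10/30 (33.3%) and iCPD 8/30 (26.7%).

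**The case against.** The best case for leaving the text alone is that little depends on it. Both categories are non-response, and neither counts as disease control. No estimate, interval or decision changes. The parallel RECIST 1.1 rows still show PD for every progressor with nothing better, because RECIST 1.1 has a single progression category. Protocol 9.2.4 also plans listings of tumor measurements and BOR, from which the split might be recovered. All of this stands as a limit on size, although SAP section 8 does not repeat those listings.

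A reader might infer that the rule defeats the purpose of iRECIST in this trial. The documents do not support that. SAP 8.2 and Appendix 1 give the purpose as avoiding premature discontinuation when progression may be a transient flare. A flare followed by iSD, iPR or iCR is still classified correctly.

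A reader might also infer that the iCPD row is zero whatever is in the database. That is slightly too strong. An iCPD recorded with no prior iUPD could enter the row, but such a record would depart from Appendix 1.

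What the objection does not answer is that SAP 8.3 asks for an iCPD count which SAP 8.2 makes impossible under correct recording. Nothing else in the SAP lets a confirmed progression replace the earlier iUPD.

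**Conclusion.** The rule is wrong as written, with a narrow effect. Provided responses are recorded as Appendix 1 requires, no subject can have iCPD as iBOR, and every confirmed progressor with no iCR, iPR or iSD appears as unconfirmed. The iUPD row then mixes at least three kinds of subject: those with confirmed progression, those re-imaged with persistent iUPD, and those never re-imaged. The last group includes clinically unstable subjects, for whom Appendix 1 does not require a repeat scan, and any subject who leaves the study before one.

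The error does not reach all confirmed progressors: one with an earlier iSD, iPR or iCR is properly reported under that category. Nor does it reach the efficacy conclusions, since iORR with its interval, RECIST 1.1 BOR and the primary ORR are the same under either rule. How many subjects would move cannot be determined from the documents and could be none.

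**What to change.** Add one sentence to SAP 8.2 after the iBOR definition:

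*A subject with no iCR, iPR or iSD in the iBOR window is assigned iCPD if an iUPD is confirmed as iCPD within that window (the iCPD assessment itself is included), and iUPD only if progression was not confirmed within it.*

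The wording keeps the existing window, so a confirmatory scan after end of treatment would still not count. SAP 8.2 does not say which date marks end of treatment; the programming specification should name it, because a confirmatory scan may come after the last dose.

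The six rows in SAP 8.3 can stay as they are. The cost is a sentence of SAP text and a small change to the iBOR derivation. It needs no new data, since Appendix 1 says the iRECIST assessments are held in the clinical database.
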